9.1 Evaluation During Protocol Treatment

	Investigations	Timing
History and Physical Exam including:	
 history weight ECOG Performance status vital signs (blood pressure and pulse) clinical tumour measurements (if applicable) 	Day 1 each cycle
Hematology*	
 CBC, differential, platelets 	Day 1 each cycle
Biochemistry*	
 electrolytes (sodium, potassium, chloride, bicarbonate) alkaline phosphatase AST, ALT serum creatinine bilirubin 	Day 1 each cycle
	
 phosphorous calcium magnesium albumin 	As clinically indicated
	
 TSH, FT3, FT4 	Every other cycle
Radiology**	
 CT scan with contrast of chest, abdomen/pelvis Other sites as clinically indicated 	4 weeks, 12 weeks, then every 12 weeks
Other Investigations	
 ECG 	As clinically indicated
Economics	
 Health Utilities Index (EQ-5D) Resource Utilization Assessment 	To be completed at each 12 weekly visit until progression OR maximum 1 year from registration
Adverse Events***	Patients must be evaluated after each cycle for adverse events	

* Bloodwork Timing: Pre-treatment blood draws should be done within 72 hours (maximum) prior to treatment.

** Patients with a CR or PR should have scans repeated after minimum 4 weeks to confirm response. See Appendix VII for CT requirements.

*** Adverse events will be recorded and graded according to the NCI Common Terminology Criteria for Adverse Events (CTCAE) (Appendix V).

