Complete Response (CR): disappearance of *target* and *non-target* lesions and normalization of tumour markers. Pathological lymph nodes must have short axis measures < 10 mm (*Note*: continue to record the measurement even if < 10mm and considered CR). Residual lesions (other than nodes < 10 mm) thought to be non-malignant should be further investigated (by cytology specialized imaging or other techniques as appropriate for individual cases *[Eisenhauer 2009]* before CR can be accepted. Confirmation of response is only required in non-randomized studies.

Partial Response (PR): at least a 30% decrease in the sum of measures (longest diameter for tumour lesions and short axis measure for nodes) of target lesions, taking as reference the baseline sum of diameters. Non target lesions must be non-PD. Confirmation of response is only required in non-randomized studies.

Stable Disease (SD): Neither sufficient shrinkage to qualify for PR nor sufficient increase to qualify for PD taking as reference the smallest sum of diameters on study.

Progressive Disease (PD): at least a 20% increase in the sum of diameters of measured lesions taking as references the smallest sum of diameters recorded on study (including baseline) AND an absolute increase of $\geq 5\text{mm}$. Appearance of new lesions will also constitute progressive disease (including lesions in previously unassessed areas). In exceptional circumstances, unequivocal progression of non-target disease may be accepted as evidence of disease progression, where the overall tumour burden has increased sufficiently to merit discontinuation of treatment or where the tumour burden appears to have increased by at least 73% in volume. Modest increases in the size of one or more non-target lesions are NOT considered unequivocal progression. If the evidence of PD is equivocal (target or non-target), treatment may continue until the next assessment, but if confirmed, the earlier date must be used.

Patients that are clinically well may continue on therapy following RECIST progression with new lesions or increase in target lesions if the increase in disease burden does not meet the definition of PD by immune response criteria *[Seymour 2016]*. In this situation, patients do not have unequivocal progression until immune response criteria are met (see Table 2 below).

AMEND #1: 2016-NOV-23

Table 1: Integration of Target, non-Target and New Lesions into Response Assessment:

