Target Lesions	Non-Target Lesions	New Lesions	Overall Response	Best Response for this Category also Requires
Target lesions ± non target lesions				
CR	CR	No	CR	Normalization of tumour markers, tumour nodes <10mm
CR	Non-CR/Non-PD	No	PR	
CR	Not all evaluated	No	PR	
PR	Non-PD/ not all evaluated	No	PR	
SD	Non-PD/ not all evaluated	No	SD	documented at least once \geq 4 wks. from baseline
Not all evaluated	Non-PD	No	NE	
PD	Any	Any	PD	
Any	PD	Any	PD	
Any	Any	Yes	PD	
Non target lesions ONLY				
No Target	CR	No	CR	Normalization of tumour markers, tumour nodes < 10mm
No Target	Non-CR/non-PD	No	Non-CR/non-PD	
No Target	Not all evaluated	No	NE	
No Target	Unequivocal PD	Any	PD	
No Target	Any	Yes	PD	
Note: Patients with a global deterioration of health status requiring discontinuation of treatment without objective evidence of disease progression at that time should be reported as "symptomatic deterioration". This is a reason for stopping therapy, but is NOT objective PD. Every effort should be made to document the objective progression even after discontinuation of treatment.				

Immune-Related Response Assessment

Overall response will also be assessed using iRECIST [Seymour 2016]. Immunotherapeutics may result in infiltration of immune cells leading to transient increase in the size in malignant lesions, or undetectable lesions becoming detectable. The criteria are identical to those of RECIST 1.1 in many respects but have been adapted to account for instances where an increase in tumour burden, or the appearance of new lesions, does not reflect true tumour progression.

Key differences are described below. All responses defined using iRECIST criteria are designated with a prefix. iRECIST time-point and best overall responses will be recorded separately.

AMEND #1: 2016-NOV-23

Confirming Progression

Unlike RECIST 1.1, iRECIST requires the confirmation of progression and uses the terms iUPD (unconfirmed progression) and iCPD (confirmed progression). Confirmatory scans should be performed at least 4 weeks, but no longer than 8 weeks after iUPD.

iCPD is confirmed if further increase in tumour burden, compared to the last assessment, is seen as evidenced by one or more of the following:

- Continued increase in tumour burden (from iUPD) where RECIST 1.1 definitions of progression had been met (from nadir) in target, non-target disease or new lesions
 - Progression in target disease worsens with an increase of at least 5 mm in the absolute value of the sum

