 - Continued unequivocal progression in non-target disease with an increase in tumour burden
 - Increase in size of previously identified new lesion (s) (an increase of at least 5 mm in the absolute value of the sum of those considered to be target new lesions) or additional new lesions.
- RECIST 1.1 criteria are met in lesions types (target or non-target or new lesions) where progression was not previously identified, including the appearance of additional new lesions.

If iUPD is not confirmed at the next assessment, then the appropriate response will be assigned (iUPD if the criteria are still met, but no worsening, or iSD, iPR or iCR if those criteria are met compared to baseline). As can be seen in table 2, the prior documentation of iUPD does not preclude assigning iCR, iPR, or iSD in subsequent time-point assessments or as best overall response (BOR) providing that iCPD is not documented at the next assessment after iUPD.

New Lesions

New lesions should be assessed and measured as they appear using RECIST 1.1 criteria (maximum of 5 lesions, no more than 2 per site, at least 10 mm in long axis (or 15 mm in short axis for nodal lesions), and recorded as New Lesions-Target (NLT) and New Lesion-Non-Target (NLNT) to allow clear differentiation from baseline target and non-target lesions.

New lesions may either meet the criteria of NLT or NLNT to drive iUPD (or iCPD). However, the measurements of NLT should NOT be included in the sum of measures of original target lesions identified at baseline. Rather, these measurements will be collected on a separate table in the case record form.

PD is confirmed in the New Lesion category if the next imaging assessment, conducted at least 4 weeks (but not more than 8 weeks) after iUPD confirms further progression from iUPD with either an increase of at least 5 mm in the absolute value of the sum of NLT OR an increase (but not necessarily unequivocal increase) in the size of NLNT lesions OR the appearance of additional new lesions.

AMEND #1: 2016-NOV-23

Table 2: Time-point (TP) iResponse

Target Lesions*	Non-Target Lesions*	New Lesions*	Time Point Response	
			No prior iUPD**	Prior iUPD**; ***
iCR	iCR	No	iCR	iCR
iCR	Non-iCR/Non-iUPD	No	iPR	iPR
iPR	Non-iCR/Non-iUPD	No	iPR	iPR
iSD	Non-iCR/Non-iUPD	No	iSD	iSD

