iUPD with no change OR decrease from last TP	iUPD with no change OR decrease from last TP	Yes	NA	NLs confirms iCPD if NLs were previously identified and increase in size (≥ 5 mm in SOM for NLT or any increase for NLNT) or number. If no change in NLs (size or number) from last TP, remains iUPD
iSD	iUPD	No	iUPD	Remains iUPD unless iCPD confirmed based in further increase in size of NT disease (need not meet RECIST 1.1 criteria for unequivocal PD)
iUPD	Non-iCR/Non-iUPD	No	iUPD	Remains iUPD unless iCPD confirmed based on: 
 o further increase in SOM of at least 5 mm, otherwise remains iUPD
iUPD	iUPD	No	iUPD	Remains iUPD unless iCPD confirmed based on further increase in: 
 o previously identified T lesion iUPD SOM ≥ 5 mm and / or o NT lesion iUPD (prior assessment - need not be unequivocal PD)
iUPD	iUPD	Yes	iUPD	Remains iUPD unless iCPD confirmed based on further increase in: 
 o previously identified T lesion iUPD ≥ 5 mm and / or o previously identified NT lesion iUPD (need not be unequivocal) and /or o size or number of new lesions previously identified
Non-iUPD/PD	Non-iUPD/PD	Yes	iUPD	Remains iUPD unless iCPD confirmed based on 
 o increase in size or number of new lesions previously identified

* Using RECIST 1.1 principles. If no PSPD occurs, RECIST 1.1 and iRECIST categories for CR, PR and SD would be the same.

** In any lesion category.

*** Previously identified in assessment immediately prior to this TP.

AMEND #1: 2016-NOV-23

Table 3: iRECIST Best Overall Response (iBOR)

All patients will have their iBOR from the start of study treatment until the end of treatment classified as outlined below.

TPR1	TPR2	TPR3	TPR4	TPR5	iBOR
iCR	iCR, iPR, iUPD, NE	iCR, iPR, iUPD, NE	iUPD	iCPD	iCR
iUPD	iPR, iSD, NE	iCR	iCR, iPR, iSD, iUPD, NE	iCR, iPR, iSD, iUPD, iCPD, NE	iCR
iUPD	iPR	iPR, iSD, iUPD, NE	iPR, iSD, iUPD, NE, iCPD	iPR, iSD, iUPD, NE, iCPD	iPR
iUPD	iSD, NE	PR	iPR, iSD, iUPD, NE	iPR, iSD, iUPD, iCPD, NE	iPR
iUPD	iSD	iSD, iUPD, NE	iSD, iUPD, iCPD, NE	iSD, iUPD, ICPD, NE	iSD
iUPD	iCPD	Anything	Anything	Anything	iCPD
iUPD	iUPD	iCPD	Anything	Anything	iCPD
iUPD	NE	NE	NE	NE	iUPD

- Table assumes a randomized study where confirmation of CR or PR is not required.
- NE = not evaluable that cycle.
- Designation “I” for BOR can be used to indicate prior iUPD to aid in data interpretation.

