13.0 CENTRAL REVIEW PROCEDURES

13.1 Central Radiology Review

At the conclusion of the trial, a central review of x-rays and/or scans will be carried out for response. CT scans will be reviewed and analyzed for texture analysis. For purposes of reporting, the results of both local and central radiology reviews will be included.

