APPENDIX VI - CT FOR TEXTURE ANALYSIS

CT for Texture Analysis (Baseline, 4 weeks, 12 weeks then every 12 weeks)

CT Platform: CT exam should be performed on the same multi-slice CT scanner model within the same institution.

Intravenous contrast: Patients must undergo CT with intravenous contrast unless there is a contrast allergy that has developed after the baseline scan, in which case, the subsequent scans will be performed without intravenous contrast.

Coverage: Chest, abdomen and pelvis

Scan parameters for baseline, 4 weeks, 12 weeks then every 12 weeks:

Coverage:

1. Arterial and portal phase abdomen as per local protocol
2. Pelvis post contrast
3. Chest post contrast

Contrast: Administered as per local protocol with a single bolus

Other Parameters:

Slice thickness: 5 mm, reconstruction 2.5 mm

CT Radiation Dose and Dose Reduction Method:

If the CT scanner utilized has dose reduction capabilities (i.e. Auto-mA) these should be set for minimal dose reduction to help minimize noise related artifacts. Radiation dose saving approaches which may be in use such as those for renal colic or young adults or pediatric patients should not be used.

Central Review

All CT scans performed on trial at baseline, 4 weeks, 12 weeks then every 12 weeks should be saved to DVD/CD and sent for central review with an imaging CT form (posted on the IND 225 webpage) to:

[name]
Sunnybrook Health Sciences Centre
[name]
[name]
[name]

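### Appendix VI asks sites to send only the scheduled CT for central review, so some scans that decide response or progression are not requested (minor)

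*Combined protocol and SAP*

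**What the plan says.** - **Central review.** Section 13.1 states that at the end of the trial "a central review of x-rays and/or scans will be carried out for response", that CT will be analysed for texture, and that "the results of both local and central radiology reviews will be included".
- **What sites send.** Appendix VI, under Central Review: "All CT scans performed on trial at baseline, 4 weeks, 12 weeks then every 12 weeks should be saved to DVD/CD", and sent to the central site. The coverage given there is chest, abdomen and pelvis. No other image-transfer instruction appears in the protocol. The appendix mentions an imaging form on the trial webpage, which is not reproduced. Appendix IV collects radiology reports, not images.
- **Other imaging.** Section 9.1 adds "Other sites as clinically indicated". No scheduled scan covers the brain, although Section 5.2.4 admits patients with stable brain metastases.
- **Progression.** Section 10.2.5: "Appearance of new lesions will also constitute progressive disease (including lesions in previously unassessed areas".
- **iRECIST confirmation.** "Confirmatory scans should be performed at least 4 weeks, but no longer than 8 weeks after iUPD".
- **Response confirmation.** Section 9.1 asks for a repeat scan at least 4 weeks after CR or PR, with no upper limit. Section 10.2.5 requires confirmation in non-randomized studies, which this is.

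**The concern.** The central review can read only the images it receives. If a site follows Appendix VI to the letter, three kinds of scan that may set the local result do not reach the central reader: imaging of the brain or another unscheduled site, the iUPD confirmation scan, and an off-schedule scan confirming CR or PR.

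The two readings are to be reported together. A reader of the results would naturally take a difference between them as a difference in interpretation, when part of it could come from the central reader never having had the deciding image. The responder label is the grouping variable for the primary texture objective. Response rate and duration of response are secondary outcomes. Section 2 also hopes that texture will separate pseudoprogression from true progression, and the iUPD confirmation scan is the protocol's means of telling these apart.

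**Working it through.** The plan gives no figure for how many scans or patients fall outside the Appendix VI list, so there is nothing to reproduce on that point. The check is of the schedule, then of three patient sequences, then of possible size.

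**1. iUPD windows against the schedule.** Scheduled on-study CT (Section 9.1): weeks 4, 12, 24, 36, 48. Window = iUPD week + 4 to iUPD week + 8 (Section 10.2.5).

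| iUPD first seen | Window (weeks) | Scheduled CT inside | Next scheduled CT |
|---|---|---|---|
| 4 | 8-12 | week 12, on the edge | 12 |
| 12 | 16-20 | none | 24 |
| 24 | 28-32 | none | 36 |
| 36 | 40-44 | none | 48 |
| 48 | 52-56 | none | 60, off protocol |

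From week 12 on, 0 of 4 windows contain a scan that sites are asked to send. The last row adds little, because Section 12.2 caps protocol treatment at one year.

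**2. What a missing iUPD confirmation scan changes.** If progression is not confirmed at the next assessment, the status becomes "iUPD if the criteria are still met, but no worsening, or iSD, iPR or iCR if those criteria are met compared to baseline". Table 2 takes prior iUPD from the assessment immediately before. Suppose iUPD at week 12, iSD at week 16, and at week 24 target progression with a sum at least 5 mm above week 12. Locally, week 24 is a new iUPD. Without the week 16 image, the central reader would call week 24 iCPD, or leave it as iUPD if the 8-week limit is enforced.

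**3. What a missing brain scan changes.** Suppose PR on the week 4 CT, a new brain lesion on a symptom-driven scan at week 7, and PR on the week 12 CT. The scans sent show PR confirmed at week 12. Under Table 1, any new lesion gives PD locally at week 7. Under iRECIST, the four rows of Table 2 that give iCR, iPR or iSD all have no new lesion. A persisting, unchanged brain lesion therefore falls under "Remains iUPD unless iCPD confirmed based on" growth or further lesions. The responder label is at risk only if the brain finding precedes confirmation: before week 4 + 4 = 8 or week 12 + 4 = 16 at the earliest, or before week 12 or 24 if the next scheduled CT confirms.

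**4. What a missing CR/PR confirmation scan changes.** Suppose PR at week 12, confirmed at week 16, and PD at week 24. Locally this is a confirmed PR; from the scans sent, it is an unconfirmed PR followed by PD. If PR still holds at week 24, that CT confirms it and nothing is lost.

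**5. Size for the primary comparison (assumptions).** Inputs: 80 evaluable patients and a 35% response rate (Section 14.2), so 0.35 x 80 = 28 responders and 52 non-responders. Section 14.2 prints 20-25 and 55-60, which does not match 35%; this point does not depend on it. Assume a true AUC of 0.70, and m patients who are responders on one reading and non-responders on the other. For the reading that moves them:

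AUC = (52 x 0.70 + m x 0.50) / (52 + m)

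- m = 0: 0.700
- m = 1: 36.9/53 = 0.696
- m = 2: 37.4/54 = 0.693
- m = 3: 37.9/55 = 0.689

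The response rate on that reading is (28 - m)/80: 35.0%, 33.8%, 32.5% and 31.3%. Starting from 25 versus 55 instead, m = 3 gives (38.5 + 1.5)/58 = 0.690. The Hanley-McNeil standard error at AUC 0.70 with 28 versus 52 is about 0.064, so a shift of 0.011 is under one-fifth of a standard error.

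**6. Size for iRECIST (assumptions).** Section 2 cites 38% response and about a further 30% disease control in an earlier pembrolizumab study, leaving 32%, or 0.32 x 80 = 25.6 patients. If 25% to 75% of these first progress at week 12, that is 6.4 to 19.2 patients. Fewer would have an unsent confirmation scan, since some stop without one. Later progressions are not counted.

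**The case against.** The strongest reply is that this is an omitted submission instruction and no more. Section 13.1 sets no limit on which scans are reviewed, and the review comes at the end of the trial, so images can still be requested. Appendix VI is headed as a texture-acquisition appendix, and its list may have been written for that purpose. A brain CT done at a scheduled visit could be read as falling within it. Radiology reports already reach the sponsor, so the cases can be found. All of this stands, and it is why the point is minor. It does not remove the gap, because Appendix VI tells sites what to send and nothing else in the protocol widens it.

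Four stronger readings are tempting, and the documents do not support them.

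- *These scans cannot be read centrally.* They are not requested; nothing bars them.
- *Every brain-only progression is an event locally and never centrally.* Section 13.1 promises central review for response, not a central time to progression. Under Section 10.6 death counts as an event, and later progression on a body CT would count too. Censoring follows Section 10.8. A central date, if derived, would more often be later than absent.
- *The week 7 brain lesion in step 3 is settled local PD.* Table 1 says PD, but Section 10.2.5 also says that clinically well patients who continue treatment are not in unequivocal progression until the immune criteria are met. PD at week 7 is one reading.
- *The primary comparison is compromised.* RECIST 1.1 progression needs no confirmation, and iUPD and iCPD are both non-response, so missing iUPD scans hardly touch it. Pseudoprogression is in the rationale, not among the Section 1 objectives.

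Which reading defines a responder is also unstated, but that would be so even if every scan were sent. It is a separate matter.

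**Conclusion.** The point holds as a minor one. Followed as written, Appendix VI leaves the central read able to miss a new-lesion PD, able to treat as unconfirmed a response that was confirmed off schedule and had progressed by the next scheduled CT, and unable to apply the iRECIST confirmation window to iUPD from week 12 on. Local and central results can then disagree for want of images.

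The schedule finding (0 of 4 windows) follows directly from the protocol. The number of patients does not: the 0 to 3 reclassified patients, the 25% to 75% first progressing at week 12 and the AUC of 0.70 are assumptions. On those assumptions the effect on the primary texture comparison is small. The iRECIST progression status and any central progression date are more exposed than the responder label.

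**What to change.** In Appendix VI, under Central Review, state:

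> Send all scheduled CT and every other scan (any site, modality or date) used to assign response, progression or its confirmation, including brain imaging and iUPD or CR/PR confirmation scans.

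For patients already enrolled, identify such scans from the radiology reports collected under Appendix IV and request the images before the end-of-trial review.

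The cost is copying and centrally reading some additional scans that already exist. No patient needs a new procedure, and neither eligibility nor the sample size changes.

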APPENDIX VII - HEALTH UTILITIES ASSESSMENT

Introduction

The assessment of overall health benefits is complicated by the need for a measure that can combine various benefits, such as overall survival and disease free survival into a single measure of benefit. Patients may value particular benefits differently. There is no obvious way to add together independently collected benefits for an individual or for a trial to yield a measure of overall benefit. Health utilities are a measure of how people value particular health outcomes. They provide a common denominator that can be combined with survival to form a measure of overall health benefits.

Such a measure of overall health benefit can then be used as part of a health economic analysis. Health economic analyses assess the benefits and costs of an intervention, for consideration whether the intervention may be worth its “costs” – including financial, toxicity, and social costs.

The collection of information about health utilities is becoming more common in clinical protocols. In clinical trials, health utilities are most often collected using a patient self-reported questionnaire.

Health utilities data can be used in a variety of ways:

- to try and achieve the best possible outcome for patients and populations
- to evaluate the extent of change in health benefits of an individual, group, or population across time
- to evaluate new treatments, technologies, and patient management strategies
- to support approval of new drug applications or patient management strategies
- to try to provide the best value for health care dollars within and across diseases and health
- to compare costs and benefits of various financial and organization aspects of health care services

In the future, approval of new therapies or patient management strategies will most likely be based on a combination of health benefit and cost data. This may be formally done using health utilities as part of a health economic analysis.

Instructions for Administration of a Health Utilities Questionnaire (see IND.225 webpage for questionnaire)

The instructions below are intended as a guide for the administration of the Health Utilities Questionnaire

1. Preamble

Health utilities data are collected for research purposes, and will not be used for the patient's individual medical care. The assessment is in the form of a self report questionnaire. Therefore, it must be completed by the patient only, without translation, coaching or suggestions as to the “correct” answer by relatives or health care personnel.

The usual scheduled times to obtain the questionnaires are as follows:

- Pre-registration (for this study, within 7 days prior to registration)
- During treatment (for this study, at each 12 weekly visit until progression OR maximum 1 year from registration)

The information provided by the patient in the completed questionnaire is confidential and should not be discussed with or shown to anyone who is NOT mentioned in the consent form signed by the patient.

If a particular question has not been answered, please document the reason(s) in the appropriate space on the questionnaire. If the whole questionnaire has not been completed, please document the reason(s) on the appropriate case report forms.

2. Pre-treatment Assessment

It should be explained to the patient that the purpose of the questionnaire is to assess the impact of treatment on different areas of the patient's life, eg: psychological distress, social disruption, symptoms, side effects, et cetera.

The Clinical Research Associate (CRA) should collect the questionnaire as soon as it has been completed, check to see that each question has been answered and gently remind the patient to answer any inadvertently omitted questions. If a patient states that s/he prefers not to answer some questions and gives a reason(s), the reason(s) should be noted on the questionnaire. If a specific reason is not given, this also should be noted on the questionnaire.

3. Assessments During Treatment

The health utilities questionnaire should be given to the patient before being seen by the doctor, and prior to treatment on the day of treatment, as required by the schedule in the protocol. If the patient does not have a doctor visit scheduled, or if it was not possible for the patient to complete the questionnaire before being seen by the doctor, s/he should still complete the questionnaire prior to treatment.

A patient may, on occasion, be reluctant to complete the questionnaire because they feel unwell. In that case, you may express sympathy that things are below par, but state that this is exactly the information we require if we are to understand more about how overall health is affected. You may also remind them that it takes only a few minutes to complete.

4. What If...

The patient should complete the questionnaires at the clinic. The exception is that the design of some trials may require the patient to take the questionnaire home with them after leaving the clinic, and complete it on the specific day, because a return visit to the clinic is not scheduled.

There may be circumstances when the patient does not complete the questionnaire as required in the clinic. A couple of situations are described below.

A. The patient leaves the clinic before the questionnaire could be administered, or someone forgets to give the questionnaire to the patient.

Contact the patient by phone informing him or her that the questionnaire was not completed. As the patient is s/he is willing to complete one:

If yes, mail a blank questionnaire to the patient, and make arrangements for return of the questionnaire in a timely fashion. Record the date it was mailed and the date received on the questionnaire.

If this is not feasible, then ask the patient if s/he is willing to complete a questionnaire over the phone. If the patient agrees, read out the questions and range of possibilities, and record the answers. Make a note on the questionnaire that the questionnaire was completed over the phone.

If no, note the reason why the questionnaire was not completed on the appropriate case report form.

B. The patient does not want to complete the questionnaire in clinic.

Should the patient not wish to answer the questionnaire in the clinic but insists on taking it home, and failing to comply with the patient's wishes is likely to result in the questionnaire not being completed at all, then the patient may take the questionnaire home with instructions that it is to be completed the same day. When the questionnaire is returned, the date on which the questionnaire was completed should be noted and a comment made on the questionnaire as to why the patient took it away from the clinic for completion.

5. Inability to Complete Health Utilities Questionnaire (for reason other than illiteracy in English or French)

